# **STUDY PROFORMA**

SERIAL NO:
BIODATA:
(1) NAME:
(2) PHONE NUMBER:
(3) AGE: (4) SEX:
(5) OCCUPATION:
OTHER INFORMATION:
(6A) LEVEL OF EDUCATION: UNEDUCATED ( ) PRIMARY ( ) SECONDARY( ) TERTIARY ( )
(6B)(ROUTE OF ADMISSION: ED ( ) CLINIC ( ) OTHERS
(6C)WARD: ED ( ) ICU ( ) MEDICAL ( ) SURGICAL ( ) GYNAECOLOGIC ( ) PAEDIATRICS ( )
CLINICAL FEATURES:
(7) COMPLAINT: COUGH ( ) CHEST PAIN ( ) BREATHLESSNESS ( ) TRAUMA ( ) FEVER ( ) RECURRENT ( ) OTHERS
(8) OTHER SYSTEMIC AND ORGAN INVOLVEMENT:
(9) CO-MORBIDITIES: HYPERTENSION ( ); DURATION (years)
DIABETES ( ); DURATION (years)
CHRONIC LIVER DISEASE ( ) ; DURATION (years)
SKIN LESIONS ( ); TYPE; DURATION (years)
CHRONIC KIDNEY DISEASE (); DURATION (years)
CALCULATED CHARLESON COMORBIDITY INDEX
OTHERS DURATION:

SERIAL NO: .....

(10) TREATMENT AND DRUG HISTORY:

[figure not shown]
CHEMOTHERAPY: SPECIFY DRUGS AND DOSE

	_; DURATION
; LAST COURSE	
IRRADIATION: SITE; HOW MANY FRACTIONS TA	
STERIODS: Y/N IF YES, DOSE;DURATION	
(11) HISTORY OF WOUND FAILURE: KELOIDS Y/N HYPERTROPHI	C SCARS Y/N
(12) PREVIOUS CHEST TUBE INSERTION: YES ( )	NO ( )
ADVERSE EFFECT OF PREVIOUS CHEST TUBE: Y/N IF YES, WHICH REACTION?	[
(13) CIGARRETTE SMOKING: YES ( ) NO ( )	
IF YES, NUMBER OF PACK YEARS:	
(14) ALCOHOL INTAKE: Y/N , IF YES, DURATION IN YRS	
ESTIMATED QUANTITY(BOTTLES AND FREQUENCY)	
EXAMINATION FINDINGS:	
(14) PALOR: YES ( ) NO ( )	
(15) SKIN TURGOR: $<2s()$ $>2s()$	
(16) DYSPNOEA: YES ( ) NO ( ) NYHA CLASS I, I	I, III, IV
(17) NEOPLASTIC CHEST WALL DISEASE: YES ( ) NO ( )	
AFFECTED SIDE: SAME SIDE ( ) CONTRALATERAL SI	DE ( )
(18) SKIN LESION:	
LACERATION: YES ( ) NO ( ), IF YES, LOCATION	
SKIN CONTUSION: YES ( ) NO ( ), IF YES, LOCATION	
AVULSION: YES ( ) NO ( ), IF YES, LOCATION	
OTHERS:	
AFFECTED SIDE: SAME SIDE ( ) CONTRALATERAL SI	DE ()

SERIAL NO:		
(19) THORACOCENTESIS: PURULENT ( )	SEROUS ( ) SEROPU HAEMORRHAGIC ( ) S	JRULENT ( ) EROSANGUINOUS ( )
(20) WEIGHT	HEIGHT BM	Π
INVESTIGATION:		
(21) PCV:		
(22) SERUM PROTEIN:	; SERUM ALBUMIN	
(23) CHEST X-RAY FINDING	S	
(24) CHEST CT SCAN FINDIN	IGS	
(25) PLEURAL FLUID GENE 2	XPERT REACTIVE: YES ()	NO ( )
(26) PLEURAL FLUID CYTOL	LOGY: MALIGNANT () IN	NFLAMMATORY ()
(27) PLEURAL BIOPSY HISTO	DLOGY REPORT:	
(28) OTHER RELEVANT INV		
CHEST TUBE MANAGEME	NT:	
(29) SITE OF CHEST TUBE IN	ISERTION: RIGHT ()	EFT ( )
INTERCOSTAL SPACE		
(30) SIZE OF CHEST TUBE IN	\ FR:	
(31) USE OF PROLENE PURS	E STRING: YES ()	NO ( )
(32) DURATION OF CHEST T	UBE RETENTION:	
(33) USE OF THERAPEUTIC A	ANTIBIOTICS YES() NO()	
IF YES, INDICATE THE GENE	ERIC TYPE , DOSE, FREQUENCY	AND DURATION IN DAYS
	R CHEST TUBE INSERTION):	,
PNEUMOTHORAX:	YES()	NO ( )
TUBE DISLOGDEMEN		NO ( )

SERIAL NO: .....

EMPYEMA:	YES ( )	NO ( )
WOUND INFECTION:	YES ( )	NO ( )
WOUND DEHISCENCE:	YES ( )	NO ( )
FLUID LEAKAGE:	YES ( )	NO ( )
AIR LEAK:	YES ( )	NO ( )
PAIN:	YES ( )	NO ( )

PAIN SCORE: DAY 1	6AM ( )	6PM( )
DAY 2	6AM ( )	6PM( )
DAY 3	6AM ( )	6PM( )
DAY 4	6AM ( )	6PM( )
DAY 5	6AM ( )	6PM( )
DAY 6	6AM ( )	6PM( )
DAY 7	6AM ( )	6PM( )
DAY 8	6AM ( )	6PM( )
DAY 9	6AM ( )	6PM( )
DAY 10	6AM ( )	6PM( )

# SERIAL NO: .....

(35) COMPLICATIONS (IMMEDIATELY AFTER CHEST TUBE REMOVAL):

PNEUMOTHORAX ON IMMEDIATE POST-TUBE REMOVAL CHEST XRAY: YES ( ) NO ( )

PNEUMOTHORAX ON CHEST XRAY DONE AFTER 1 WEEK:

	YES ( )	NO ( )
EMPYEMA:	YES ( )	NO ( )
WOUND INFECTION:	YES ( )	NO ( )
WOUND DEHISCENCE:	YES ( )	NO ( )
FLUID LEAKAGE:	YES ( )	NO ( )
AIR SUCK-IN THROUGH WOUN	ID:	
	YES ( )	NO ( )
MAJOR PAIN:	YES ( )	NO ( )
PAIN SCORE:		
DAY 1	6AM ( )	6PM()
DAY 2	6AM ( )	6PM()
DAY 3	6AM ( )	6PM()
DAY 4	6AM ( )	6PM()
DAY 5	6AM ( )	6PM()
DAY 6	6AM ( )	6PM()
DAY 7	6AM ( )	6PM()
DAY 8	6AM ( )	6PM()
DAY 9	6AM ( )	6PM()
DAY 10	6AM ( )	6PM( )

### (36) COMPLICATIONS AT FOLLOW-UP 1

PNEUMOTHORAX ON FOLLOW UP CHEST XRAY:

	YES ( )	NO ( )
WOUND INFECTION:	YES ( )	NO ( )
WOUND DEHISCENCE:	YES ( )	NO ( )

SERIAL NO:		
HYPERTROPHIC SCAR:	YES ( )	NO ( )
KELLOID:	YES ( )	NO ( )
WOUND PAIN:	YES ( )	NO ( )
IF YES, PAIN SCORE:		

# COMPLICATIONS AT FOLLOW-UP 2

WOUND INFECTION:	YES ( )	NO ( )
WOUND DEHISCENCE:	YES ( )	NO ( )
HYPERTROPHIC SCAR:	YES ( )	NO ( )
KELLOID:	YES ( )	NO ( )
WOUND PAIN:	YES ( )	NO ( )
IF YES, PAIN SCORE:		
PAIN SCORE:	6AM ( )	6PM ( )

# COMPLICATIONS AT FOLLOW-UP 3

WOUND INFECTION:	YES ( )	NO ( )
WOUND DEHISCENCE:	YES ( )	NO ( )
HYPERTROPHIC SCAR:	YES ( )	NO ( )
KELLOID:	YES ( )	NO ( )
WOUND PAIN:	YES ( )	NO ( )
IF YES, PAIN SCORE:		
PAIN SCORE:	6AM ( )	6PM ( )

# COMPLICATIONS AT FOLLOW-UP 4

WOUND INFECTION:	YES ( )	NO ( )
WOUND DEHISCENCE:	YES ( )	NO ( )
HYPERTROPHIC SCAR:	YES ( )	NO ( )
KELLOID:	YES ( )	NO ( )

SERIAL NO:		
WOUND PAIN:	YES ( )	NO ( )
IF YES, PAIN SCORE:	·	
PAIN SCORE:	6AM ( )	6PM ( )
COMPLICATIONS AT FOLLO	W-UP 5	
WOUND INFECTION:	YES ( )	NO ( )
WOUND DEHISCENCE	E: YES()	NO ( )
HYPERTROPHIC SCAF	R: YES ( )	NO ( )
KELLOID:	YES ( )	NO ( )
WOUND PAIN:	YES ( )	NO ( )
IF YES, PAIN SCORE	:	
PAIN SCORE:	6AM ( )	6PM ( )

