# STUDY VARIABLES AND DEFINITION

The independent variables to be employed for the analysis include:

- Age of the patient
- Sex of the patient
- Presence of specific co-morbidities (Diabetes, Hypertension, Chronic Liver disease, Chronic kidney disease)
- Charleson Comorbidity Index
- History of cigarette smoking and estimated pack years if positive

- Use of steroids and chemotherapeutic agent
- Abnormal Body mass index (Obesity(BMI> 30kg/m^2), Malnutrition(BMI< 18kg/m^2)

The Dependent variables to be employed for the analysis include:

- Presence of severe pain at the chest tube site after chest tube insertion (Average daily pain score after tube insertion > 5 on the Visual Analog Scale and or Numerical Rating Scale)
- Occurrence of tube dislodgement after chest tube insertion
- Occurrence of peri-tubal leakage of fluid after chest tube insertion
- Presence of wound air suck-in after chest tube removal (indicated by presence of air suck-in sound through the wound into the pleural space during quiet and or forced inspiration)
- Occurrence of wound infection after chest tube removal (presence of purulent or offensive wound discharge with or without fever or presence of wound discharge that is microbiologically positive)
- Occurrence of wound dehiscence after chest tube removal
- Occurrence of early (within 7 days) and late pneumothorax (more than 1 week) after chest tube removal confirmed on chest radiography
- Development of raised or elevated thoracostomy wound scars (unsightly scars appearing like hypertrophic scars or keloids) within 3 months of chest tube removal

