# **RESEARCH QUESTIONS**

- What is the difference in the tube-related complication rates after placing a purse-string suture (U suture placement and retention) for thoracostomy wound re-approximation versus non-placement of purse-string at the time of chest tube insertion?
- What is the difference in the early and late complication rates after using a purse-string suture (U suture) for thoracostomy wound re-approximation versus use of only an occlusive adhesiveabsorbent dressing with unreapproximated thoracostomy wound edges; at the time of chest tube removal?
- What is the difference in pain score after using a purse-string suture (U suture) for thoracostomy wound re-approximation versus use of only an occlusive adhesive-absorbent dressing with unreapproximated thoracostomy wound edges; after chest tube removal?
- Is purse-string thoracostomy wound closure associated with more cosmetic complications of thoracostomy scar in the long term than un-reapproximated thoracostomy edges with an occlusive adhesive-absorbent dressing ?

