# SAMPLING AND RANDOMISATION TECHNIQUES

A block but balanced randomization technique (Unstratified) will be used in determining the use or otherwise of purse-string in the study population. Randomization and intervention assignment into either of the two groups A or B (purse string versus non-purse string) will be determined by grouping labels (A or B) and serialization generated by the soft-ware Winpepi from number 1 to 142 (i.e. Random assignment of 71 in Group A and 71 in Group B).

The generated sequence will be stored on the computer of a blinded research assistant who will be required to inform the team of the next assigned intervention according to the generated sequence, at the time of chest tube insertion for all included and consenting patients. The research assistant will keep record of all assigned labels and ensure all intervention assignment follows the computer-generated sequence in an uninterrupted and reproducible manner.

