# 3) Management of indwelling chest tubes

A chest radiograph will be done immediately after to ascertain the position of the tube and the degree of lung re-expansion. The drainage of the effluent is measured daily and charted; analgesia (combination of 1g oral paracetamol administered every 6hours at 6am, 12 noon, 6pm and 12 midnight; 50mg oral diclofenac sodium administered every 12hours at 10am and 10pm; and 50mg oral tramadol or 5mg oral morphine administered every 6hours at 9am, 3pm, 9pm and 3am) will be instituted for all patients in compliance with current unit analgesic protocol. All patients requiring therapeutic antibiotics (commenced empirically or with culture sensitivity guidance) will have the antibiotics administered according to the posology of the index medication. This category includes post-operative patients who have had chest tube inserted as an adjunct to surgery and those with any other indication for therapeutic antibiotics. All patients will have incentive spirometry (done with the standard threeball incentive spirometer, once every hour) and passive physiotherapy (three times a day). Daily dressing of the chest tube site will be done by the unit doctors during the daily ward rounds using 10% povidone iodine as described above. The pain intensity (pain scores) of the patients will be assessed at regular intervals (atleast twice a day; during morning and evening ward rounds) using the visual analogue scale (VAS), numeric rating scale (NRS) and Categorical verbal rating scale (VRS). Even though the VAS and the NRS have been shown to be superior to the VRS in the assessment of acute post-operative pain, all three will be employed in this study to enhance accuracy of assessment and minimize effect of subjectivity on observed pain scores as depicted in Figure 2 below (45).

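### No pain intensity score is taken before chest tube insertion, so the pain comparisons cannot be adjusted for starting pain intensity and lose some precision

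*Combined protocol and SAP*

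**What the plan says.** **Before insertion.** Item 7 of the Study Proforma lists presenting complaints to be ticked: "COMPLAINT: COUGH ( ) CHEST PAIN ( ) BREATHLESSNESS ( ) TRAUMA". Chest pain is present or absent, with no intensity. The procedure section on steps before insertion asks for no pain score.

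**After insertion.** Under Management of indwelling chest tubes, "The pain intensity (pain scores) of the patients will be assessed at regular intervals", at least twice daily, on a visual analogue, a numeric and a verbal scale. The form's grid opens with "PAIN SCORE: DAY 1" in the block of complications after insertion, and a second grid starts after removal. Neither has a cell for a score before the tube.

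**Pain as an outcome.** The first dependent variable is "Presence of severe pain at the chest tube site after chest tube insertion", defined as "Average daily pain score after tube insertion > 5 on the Visual Analog Scale and or Numerical Rating Scale". The third research question is "What is the difference in pain score after using a purse-string suture (U suture) for thoracostomy wound re-approximation" against the dressing alone, after removal.

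**Design and analysis.** Eligible indications are effusion, spontaneous or traumatic pneumothorax, traumatic haemothorax, and thoracotomy for certain conditions. On allocation: "A block but balanced randomization technique (Unstratified) will be used". The independent variables do not include starting pain. The analysis section names a Cox model for complications and no between-arm model for pain scores.

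**The concern.** It is reasonable to expect pain before the tube to vary widely between, say, a patient with an effusion and one with chest trauma, and some of that difference to persist into later scores. Without a starting score this variation stays in the error term, although it has nothing to do with the suture. Unstratified allocation does nothing to even it out, and a chance difference in starting pain could be neither seen nor corrected.

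No later score can stand in. The group is disclosed before the procedure starts, and in Group A the purse-string is placed and tied at insertion. Every recorded score is therefore taken after assignment and may already reflect it. Adjusting post-removal pain for scores taken with the tube in place could remove part of the effect under study. A score missed before insertion cannot be recovered later.

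**Working it through.** **The plan's own figure.** No SD, difference, power or correlation is stated for pain. The only design figure, 71 per arm, comes from acute pneumothorax at 6% versus 1.2% (two-sided 5%, 80% power, 5% non-response). The usual two-proportion formula gives

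[1.96·√(2·0.036·0.964) + 0.842·√(0.06·0.94 + 0.012·0.988)]² / 0.048² ≈ 236 per arm,

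or 236/0.95 ≈ 249 after non-response, so 71 is not reproduced. That is a separate matter. Here 71 per arm is simply the planned number.

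**Inputs.** From the Sample Size section: n = 71 per arm and two-sided 5%. Assumed: a correlation r of 0.3 to 0.5 between a pre-insertion score and a later score, and a true difference of 0.4 SD (for example, 1 point with an SD of 2.5).

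**Formulas for a continuous score, in SD units**
- Variance factor after adjustment: 1 − r²
- Standard error of the difference: √(2(1 − r²)/71)
- Difference detectable at 80% power: (1.96 + 0.842) × standard error
- Power: Φ(0.4/standard error − 1.96)
- Unadjusted patients per arm giving the same precision: 71/(1 − r²)

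| | No adjustment | r = 0.3 | r = 0.5 |
|---|---|---|---|
| Variance factor | 1 | 0.91 | 0.75 |
| Standard error | 0.168 | 0.160 | 0.145 |
| Detectable difference | 0.47 | 0.45 | 0.41 |
| Power at 0.4 SD | 66% | 70% | 79% |
| Equivalent patients per arm | 71 | 78 | 95 |

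The confidence interval narrows by about 5% (r = 0.3) or 13% (r = 0.5). With 67 evaluable per arm (71 × 0.95), power is 64% unadjusted and 68% or 76% adjusted.

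**What the tick already offers.** Suppose, at best, that it split a normally distributed score cleanly, with a proportion q ticked. Its correlation with later pain would be r·φ(z_q)/√(q(1 − q)), which is 0.759r at q = 0.3 and 0.798r at q = 0.5. Squared, the tick would recover 58% to 64% of the variance reduction.
- At r = 0.5 the factor with the tick is 0.86 to 0.84. A score takes it to 0.75, a further cut of 11% to 12% (0.75/0.841 = 0.89; 0.75/0.856 = 0.88).
- At r = 0.3 the factor with the tick is 0.95 to 0.94. A score takes it to 0.91, a further cut of 3% to 4% (0.91/0.943 = 0.965; 0.91/0.948 = 0.960).

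A symptom tick tied to neither intensity nor site probably recovers less than this. The gain of a score over the tick alone therefore probably lies between these figures and the full 9% to 25%.

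**The case against.** The strongest reply is that the plan already captures much of what makes starting pain vary. The form has ticks for chest pain and trauma, the ward, lacerations, contusions and avulsions with their location, and imaging findings. This stands. A reader might infer that no adjustment is possible, but only adjustment for intensity is lost.

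A reader might also infer bias, since some patients will have high pain before the tube. Randomisation makes such patients equally likely in either arm. If 30% to 50% had high pain, the standard error of the between-arm difference would be √(p(1 − p)·2/71), about 8 percentage points, with a 95% range of about ±15 to 16. The unadjusted standard error already allows for imbalance of that kind.

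A third tempting reading is a large gain. At r = 0.7 the variance factor would be 0.51 and power about 92%. Nothing in the documents supports so high a value. The listed outcome is pain at the tube site, which does not exist before insertion. The incision, drainage and scheduled analgesia for everyone, escalated above a score of 5, come between the two measurements. Removal follows only once the condition has improved, so r is likely to be lower still for post-removal pain, and probably for thoracotomy patients.

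Finally, 1 − r² belongs to a linear model for scores. In a logistic model for severe pain, adjustment changes the odds ratio being estimated as well as its standard error, so the table does not apply directly. Pain also did not set the sample size. These points limit the size of the problem. They do not remove the gap, because no recorded item measures pain intensity before assignment.

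**Conclusion.** The point holds as a loss of precision. The forms and procedures as published contain no pain intensity score before insertion, and no later score can replace it. For continuous scores, the variance reduction forgone is about 9% to 25% against no adjustment, and less against adjustment for items already on the form. This rests on an assumed r of 0.3 to 0.5; the power figures also assume a difference of 0.4 SD. None of these assumptions comes from the documents. The effect on the yes/no severe-pain outcome is not quantified here. Minor to moderate: worth correcting before enrolment because it is cheap and cannot be repaired afterwards.

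**What to change.** Add one pre-insertion pain score to the proforma, on the same numeric or visual analogue scale used afterwards. Name that scale, since the text calls for three scales and the grid has one space per time point. Take the score before the research assistant is asked for the group, because the trial is open-label and the patient is told the assignment. For thoracotomy patients, take it before the operation.

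In the analysis section, specify the between-arm pain models with this score as a covariate: linear for scores, logistic for severe pain. State that scores taken with the tube in place will not be used as a baseline for post-removal pain.

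The cost is one question per patient and one model term. Some emergency patients will have no score; a missing-value indicator for this baseline covariate keeps them in the analysis. The gain will be smaller in thoracotomy patients and for post-removal pain.

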#### INSTRUMENT FOR DATA COLLECTION

Data will be collected using a 7-page structured study proforma as included below (Refer to pages 28-34).

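### The proforma has no designated pneumothorax field at follow-ups 2 to 5, although a chest film is required at every follow-up visit and late pneumothorax is a listed outcome.

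*Combined protocol and SAP*

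**What the plan says.** **Outcome.** Study Variables and Definition lists as a dependent variable "Occurrence of early (within 7 days) and late pneumothorax (more than 1 week) after chest tube removal confirmed on chest radiography". The Research Questions section asks: "What is the difference in the early and late complication rates after using a purse-string suture" compared with the occlusive dressing.

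**Films.** Procedure for chest tube removal sets the same film schedule for Groups A and B: immediately after removal, at one week, and at each outpatient visit. Follow up and treatment adherence repeats that visits are monthly, three or more in number, and that the films are taken to look for pneumothorax.

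**Instrument.** Instrument for Data Collection states: "Data will be collected using a 7-page structured study proforma as included below". No other source of outcome data is named.

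**Form.** Item 35 of the Study Proforma has a yes/no field for the immediate film and another labelled "PNEUMOTHORAX ON CHEST XRAY DONE AFTER 1 WEEK". Item 36, follow-up 1, has "PNEUMOTHORAX ON FOLLOW UP CHEST XRAY". The blocks headed "COMPLICATIONS AT FOLLOW-UP 2" and "COMPLICATIONS AT FOLLOW-UP 3", and those for follow-ups 4 and 5, ask only about wound infection, dehiscence, hypertrophic scar, keloid, wound pain and pain score.

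**The concern.** The schedule and the form disagree. The protocol has patients undergo films whose stated purpose is to detect pneumothorax, but after follow-up 1 the form gives no place to enter what the film showed.

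What is at stake is the late-pneumothorax comparison. From follow-up 2 onwards, four situations look the same in the data: a film taken and clear, a film taken and positive but not entered, a film taken and not read, and a film not taken. A late rate of zero in either arm would then be hard to interpret, although showing that late events are absent is one of the useful results this trial could give. What is not captured at the visit may not be recoverable later.

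**Working it through.** The plan gives no figure to reproduce here. The check sets the film schedule against the form, visit by visit.

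**Inputs**
- Required films after removal: immediate, week 1, and each monthly visit, with a minimum of three (Procedure for chest tube removal; Follow up and treatment adherence).
- Post-removal pneumothorax fields: immediate and one-week (item 35), and follow-up 1 (item 36).
- Follow-up blocks on the form: five. The form does not say which month each one represents, so the mapping is an assumption and is varied below.

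**Mapping 1: follow-up 1 is the month-1 visit, three visits**

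| Film | Field on form |
|---|---|
| Immediate | Item 35 |
| Week 1 | Item 35 |
| Month 1 (follow-up 1) | Item 36 |
| Month 2 (follow-up 2) | None |
| Month 3 (follow-up 3) | None |

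Films required: 2 + 3 = 5. Films with a field: 3. Films without: 5 − 3 = 2, so 2 of 5. Of the three monthly films, which fall clearly in the late class, 2 of 3 have no field.

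**Mapping 2: follow-up 1 is the month-1 visit, all five blocks used**

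Films required: 2 + 5 = 7. Films with a field: 3. Films without: 7 − 3 = 4, so 4 of 7.

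**Mapping 3: follow-up 1 is the one-week visit**

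The follow-up 1 field then duplicates the one-week field in item 35, and the monthly visits start at follow-up 2. None of the monthly films has a field. At the three-visit minimum that is 3 of 5 films.

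Mapping 1 is the natural reading, because item 35 already covers the one-week film. It is also the mildest: under every mapping at least two scheduled films per patient have no field.

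**Could another item on the form fill the gap?**
- Item 23 (chest X-ray findings) sits among the investigations that precede the chest tube section, so it records baseline findings.
- The item 34 complications concern the period after insertion, with the tube in place.
- The follow-up 2 to 5 blocks have no free-text or other-complication line.

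**Could the line have been lost when the PDF was read?** Parts of the form did not read cleanly, but this is unlikely here. Four blocks repeat the same items in the same order, each heading is followed directly by wound infection, and the corresponding line in follow-up 1 survived.

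**What the documents say about event numbers.** The Literature Review gives a late pneumothorax rate of 0% in a series closed without sutures, and no late rate for purse-string closure. The counts above are therefore shares of films, not of events.

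**The case against.** **The event might still be recorded.** A reader might infer that a late pneumothorax first seen at follow-up 2 or later is bound to be lost. The documents do not support that. The films are still required, and staff could note a finding elsewhere. The label "PNEUMOTHORAX ON CHEST XRAY DONE AFTER 1 WEEK" is also close to the definition of late pneumothorax and might be stretched to later films. It is, however, a single yes/no box in a section about the time immediately after removal, and it matches the scheduled one-week film. It cannot hold the results of several monthly films. What stands is that the form has no designated field.

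**The impact may be small.** The only late rate given is 0%, and the omission is the same for both arms. This limits the importance of the point, but does not remove it: a true zero can be claimed only if the form could have recorded something else. A reader might also infer that the gap favours one closure method. The form is identical for both groups, and nothing in the documents supports that.

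**Missing dates.** A reader might infer that the form holds no dates at all, so that the Cox analysis can use only nominal visit times. The readable text shows no removal, film or visit date, and item 32, which survives in part as "DURATION OF CHEST T", is a duration. But several headings and rows nearby are broken, so the absence of dates cannot be asserted. If real, it would affect every time-to-event outcome, and the analysis section does not name late pneumothorax as a Cox endpoint. The point is secondary and conditional on the original form.

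**Conclusion.** The concern holds as a conflict between the film schedule and the only named data form. At least two scheduled films per patient have no designated pneumothorax field: 2 of 5 at the three-visit minimum and 4 of 7 if all five blocks are used, both taking follow-up 1 as month 1. If follow-up 1 is the one-week visit, no monthly film has a field.

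The consequence is possible under-counting of late pneumothorax in both arms, and a zero after follow-up 1 that cannot be interpreted. The number of events lost is unknown and may be near zero. A reader might extend the problem to the trial's power. That does not follow: the Sample Size section rests on acute pneumothorax, and the immediate and one-week films both have fields.

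The point should be corrected, because a listed outcome is incompletely captured and the remedy is almost free.

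**What to change.** 1. Add one line to each of the follow-up 2, 3, 4 and 5 blocks: *pneumothorax on chest film: yes / no / film not done; film date*. This closes the gap under any mapping of blocks to months, and it separates a clear film from a missed one.
2. Conditional: check the original form for the tube-removal date and for the dates of the other post-removal films. If they are absent, add them, so that the 7-day cut between early and late and the Cox analysis can use actual times.
3. If events are to be classed by the date on which they were first detected, state this as an added operational rule. The present definition speaks of occurrence confirmed on radiography and does not say which date decides the class. An event that arose within 7 days but was first seen on a delayed film would be classed as late under such a rule.

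The cost is four lines and possibly a few date boxes. No extra films, visits or staff are needed.
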